#### ***10.2. Statistical Methodology***

A summary of the data will be prepared for all measurement time points.

##### **10.2.1. Within-treatment Changes**

For variables measured on a continuous scale, these summaries will include the sample size, as well as the mean, standard deviation, median, minimum, and maximum. For variables measured on a categorical scale, summaries will provide the number and percentage of eyes in each category. These summaries will be provided for all eyes completing the study.

Differences between parametric variables will be compared using a two-sample t-test. Differences between categorical variables will be compared using the 2-sample test for equality of proportions.

For non-inferiority testing, if the upper boundary of the 95th confidence interval is not greater than 0.1 logMAR, non-inferiority will be claimed.

The step-down methodology will be used on the non-inferiority endpoints in the following order:

- 1) Binocular CDVA
- 2) Binocular DCIVA
- 3) Binocular UDVA
- 4) Binocular UIVA

The correlation of total ocular and internal HOAs (especially SA) with monocular DCIVA will be evaluated using regression modelling. Findings from these models will provide an indication of whether any HOAs are statistically significantly associated with post-op DCIVA, and the strength of any such association.

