### 3. GENERAL INFORMATION

Objective	To compare binocular visual outcomes with light adjustable lens (LAL) vs. Clareon monofocal/toric IOL when both are targeting mini-monovision (-0.75 ~ -1.00 D in the non-dominant eye).  The hypothesis is that the Clareon monofocal/toric IOL with mini-monovision will provide non-inferior binocular distance vision compared to LAL mini-monovision (non-inferiority margin: 0.1 logMAR).
Test Article(s)	The Clareon™ Monofocal Intraocular Lens (Toric and Non-Toric) The Light-Adjustable Lens™
Sample size	138 subjects total (69 in each group)
Study Population	Age-related Cataract patients with $\geq 0.75$ D corneal astigmatism and without previous experience of monovision $> -1.00$ D offset.
Number of sites	One
Study Design	Single center, multi-surgeon, prospective, randomized, comparative study.
Masking	None.
Variables	Primary: Binocular corrected distance visual acuity (CDVA), 3-months postop.  Secondary: 

• Binocular uncorrected distance visual acuity (UDVA), 3-months postop.

• Binocular distance-corrected intermediate visual acuity (DCIVA) at 66cm, 3-months postop.

• Binocular uncorrected intermediate visual acuity (UIVA) at 66cm, 3-months postop.

• Monocular corrected distance visual acuity (CDVA), 3-months postop.

- Monocular uncorrected distance visual acuity (UDVA), 3-months postop.
- Monocular distance-corrected intermediate visual acuity (DCIVA) at 66cm, 3-months postop.
- Monocular uncorrected intermediate visual acuity (UIVA) at 66cm, 3-months postop.

Exploratory:

- Binocular distance-corrected near visual acuity (DCNVA) at 40cm, 3-months postop.
- Binocular uncorrected near visual acuity (UNVA) at 40cm, 3-months postop.
- Monocular distance corrected defocus curve at 3 months post-op for both eyes in LAL group and dominant eye for Clareon group.
- Binocular defocus curve at 3 months post-op (dominant eye: plano corrected, non-dominant: -1.00D)
- Manifest refraction (MRSE, residual sphere, and residual astigmatism) at postoperative day 17-28 and at 3 months post-op.
- Patient reported spectacle usage questionnaire (PRSIQ) at postoperative day 17-28 and at 3 months post-op
- Total ocular, corneal and internal HOA and SA with iTRACE for both eyes in LAL group and dominant eye for Clareon group (Objective depth of focus measurement with iTRACE for each eyes in both groups)

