## 8. STUDY DESIGN

### 8.1. ***Study Design***

This study is a single center, multi-surgeon, prospective, randomized, comparative study of binocular corrected distance visual acuity (CDVA) after successful bilateral cataract surgery. Subjects will be assessed pre-operatively, operatively and at up to 6 post-operative visits. Clinical evaluations will include administration of patient reported spectacle usage questionnaire (PRSIQ), as well as measurement of monocular and binocular visual acuities at distance, intermediate, and near, defocus curve, manifest refraction, measurement of higher order aberrations.

The primary outcome measure will be the binocular corrected distance visual acuity (CDVA), 3-months postop.

Secondary outcome measures are as follows:

- Binocular uncorrected distance visual acuity (UDVA), 3-months postop.
- Binocular distance-corrected intermediate visual acuity (DCIVA) at 66cm, 3-months postop.
- Binocular uncorrected intermediate visual acuity (UIVA) at 66cm, 3-months postop.
- Monocular corrected distance visual acuity (CDVA), 3-months postop.
- Monocular uncorrected distance visual acuity (UDVA), 3-months postop.

- Monocular distance-corrected intermediate visual acuity (DCIVA) at 66cm, 3-months postop.
- Monocular uncorrected intermediate visual acuity (UIVA) at 66cm, 3-months postop.

Exploratory outcome measures are as follows:

- Binocular distance-corrected near visual acuity (DCNVA) at 40cm, 3-months postop.
- Binocular uncorrected near visual acuity (UNVA) at 40cm, 3-months postop.
- Monocular distance corrected defocus curve at 3 months post-op for both eyes in LAL group and dominant eye for Clareon group.
- Binocular defocus curve at 3 months post-op (dominant eye: plano corrected, non-dominant: -1.00D)
- Manifest refraction (MRSE, residual sphere, and residual astigmatism) at postoperative day 17-28 and at 3 months post-op.
- Patient reported spectacle usage questionnaire (PRSIQ) at postoperative day 17-28 and at 3 months post-op
- Total ocular, corneal and internal HOA and SA with iTRACE for both eyes in LAL group and dominant eye for Clareon group (Objective depth of focus measurement with iTRACE for each eyes in both groups).
- Number of days and post-op office visits from cataract surgery to routine "release of care visit" (i.e. final lock-in for LAL group, 17-28 days after 2nd eye surgery for Clareon group).

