### **9.2.4. Postoperative UV Treatments**

LAL patients will undergo UV treatment until targeted refractive outcomes are achieved (dominant eye: plano  $\pm$  0.25D; non-dominant eye: -0.75 ~ -1.00D). All routine, usual standard of care postoperative measures should be undertaken. In addition, the subject will undergo VA, manifest refraction, and iTrace testing (Section 9.3) at these visits. Any device deficiencies or adverse events will be monitored.

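### MRSE, residual sphere and monocular uncorrected acuities are not separated by eye dominance, although the two eyes of each subject have different refractive targets

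*Combined protocol and SAP*

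**What the plan says.** The Objective in section 3 compares the two lenses "when both are targeting mini-monovision (-0.75 ~ -1.00 D in the non-dominant eye". Section 9.2.2 gives the dominant eye a target of plano ± 0.25 D and the non-dominant eye -0.75 to -1.00 D. Section 9.2.4 repeats these targets for the adjustable lens: "LAL patients will undergo UV treatment until targeted refractive outcomes are achieved".

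The refractive outcome in section 8.1 is exploratory and names no eye: "Manifest refraction (MRSE, residual sphere, and residual astigmatism) at postoperative day 17-28 and at 3 months post-op". Monocular UDVA and UIVA at 3 months are secondary and also name no eye. Sections 3 and 8.1 do specify the eye for the defocus curves and the iTrace aberration measures.

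For continuous variables, section 10.2.1 says that "these summaries will include the sample size, as well as the mean, standard deviation, median, minimum, and maximum". For categorical variables, "summaries will provide the number and percentage of eyes in each category". It then says: "These summaries will be provided for all eyes completing the study". The comparison of arms is one sentence: "Differences between parametric variables will be compared using a two-sample t-test". The plan contains no summary by dominance, no proportion of eyes on target and no achieved difference between a subject's two eyes.

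**The concern.** Raw MRSE and residual sphere have a clear meaning only relative to the eye's target. If eyes with two targets go into one mean, the result describes neither eye. Monocular UDVA and UIVA have the same difficulty: each pooled mean combines an eye aimed at distance with an eye aimed nearer.

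The trial compares two routes to the same mini-monovision, postoperative light adjustment and lens power calculation. Whether both arms arrived there is the main check that the intended comparison took place. It is also needed to interpret differences in binocular UDVA, binocular UIVA and spectacle use. As written, the plan produces no direct answer.

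**Working it through.** **Inputs.** Targets are from sections 9.2.2 and 9.2.4: dominant 0 D (± 0.25 D), non-dominant -0.75 to -1.00 D, mid-point -0.875 D. There are two eyes per subject (section 7.1) and 69 subjects per arm (section 11). The within-eye SD of MRSE, s, is not in the documents. I assume 0.30 D and show 0.25 to 0.50 D.

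**The plan's own figure.** Section 11 gives 69 per group. With margin 0.1, true difference 0.05 and SD 0.1 logMAR, 2 × (1.645 + 1.282)² × 0.1² / (0.1 - 0.05)² = 68.5, rounded up to 69, at one-sided alpha 0.05 and 90% power. It concerns visual acuity between groups and is not altered by this point.

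**1. Pooled mean.** With equal numbers of each eye, mean = (dominant + non-dominant) / 2.
- At the mid-point: (0 - 0.875) / 2 = -0.4375 D.
- Across the non-dominant range: -0.375 to -0.50 D.

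These values lie between the lower edge of the dominant target (-0.25 D) and the upper edge of the non-dominant target (-0.75 D), so they fall in neither.

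**2. Pooled SD.** SD = √(s² + (offset / 2)²).
- s = 0.30, offset 0.875: √(0.090 + 0.191) = 0.53 D.
- s = 0.25, offset 0.75: 0.45 D.
- s = 0.50, offset 1.00: 0.71 D.

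At s = 0.30 the variance is 0.281 / 0.090 = 3.1 times the within-eye variance.

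**3. Effect on the t-test.** Standard error of the arm difference, treating eyes as independent, as a plain two-sample t-test does:
- Pooled, 138 eyes per arm: 0.53 × √(2/138) = 0.064 D.
- One eye type, 69 eyes per arm: 0.30 × √(2/69) = 0.051 D.

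The pooled test has twice the eyes and still a larger standard error. A shift confined to one eye type is also halved in the pooled mean.

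**4. What the pooled summary can and cannot separate (s = 0.30).**

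| Arm | Dominant / non-dominant mean (D) | Pooled mean (D) | Pooled SD (D) | Mean offset (D) |
|---|---|---|---|---|
| On target | 0 / -0.875 | -0.44 | 0.53 | 0.875 |
| No monovision, same scatter | -0.44 / -0.44 | -0.44 | 0.30 | 0 |
| No monovision, per-eye SD 0.53 | -0.44 / -0.44 | -0.44 | 0.53 | 0 |
| Non-dominant eye short by half | 0 / -0.44 | -0.22 | 0.37 | 0.44 |

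The mean alone does not separate the first three rows. The SD separates the second from the first. It does not separate the third, because it carries both offset and scatter. The fourth row is visible in the mean.

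**5. Day 17-28.** Section 9.2.2 gives the adjustable-lens eyes one pre-operative target, closest to +0.25 D, and Table 9.2-1 places the first UV treatment at this visit. Assume the refraction is taken before that treatment has effect, and that each eye sits at its target. The arm difference is then 0.25 - 0 = 0.25 D in dominant eyes and 0.25 - (-0.875) = 1.125 D in non-dominant eyes. The pooled difference is (0.25 + 1.125) / 2 = 0.69 D, which describes neither eye and arises from the targets alone.

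**The case against.** The strongest reply is that the sentence on all eyes names the completers and does not order that the two eyes be merged. The same paragraph also governs binocular acuities and a questionnaire, for which the eye cannot be the unit, so the word is loosely used. That reading is possible. It leaves the by-eye analysis unspecified, and the same addition is needed.

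A reader might infer more than the documents support:
- **That pooled results would look identical with and without monovision.** At equal scatter the SDs differ (0.53 against 0.30 D). Matching them takes a much wider per-eye SD in the arm without monovision, or the two eyes' targets swapped, contrary to sections 9.2.2 and 9.2.4.
- **That any shortfall would be hidden.** A shortfall in the non-dominant eye alone moves the pooled mean from -0.44 to -0.22 D. To hide it in the mean, the dominant eye must drift myopic by the same amount, here out of its own range.
- **That unequal loss of dominant or non-dominant eyes will bias the comparison.** Section 10.1 does select efficacy data by eye, but nothing in the documents indicates that loss differs by dominance, and no rate is given.
- **That the main conclusions are at risk.** The primary and the other three step-down endpoints are binocular. Binocular acuities and the spectacle questionnaire also capture the functional result per subject.

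These objections limit the point. They do not supply the missing by-eye summary or the achieved offset.

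**Conclusion.** The point holds as a cheap improvement. It concerns secondary monocular UDVA and UIVA and exploratory MRSE and residual sphere. Residual astigmatism and monocular CDVA are outside it, because the intended offset is spherical and is corrected when CDVA is measured.

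On the plain reading of section 10.2.1, an on-target arm has a pooled mean MRSE of about -0.44 D (-0.375 to -0.50 D), outside both targets. That result needs only the stated targets and equal numbers of each eye. The SD of about 0.53 D and the loss of precision rest on the assumed within-eye SD of 0.30 D; the SD runs from 0.45 to 0.71 D over the ranges shown. No size can be put on the acuity variables, because the documents give no by-eye acuity figures. The day 17-28 figure rests on the timing assumption stated with it.

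**What to change.** In section 10.2.1:

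1. Summarise and compare MRSE, residual sphere, monocular UDVA and monocular UIVA separately for dominant and non-dominant eyes, at each time point at which they are analysed. Each comparison then has one eye per subject, so the two-sample t-test applies directly. If both eyes enter one model, allow for correlation within subject.
2. Add the inter-eye MRSE difference (dominant minus non-dominant) per subject at Visit 8, by arm. A subject with both eyes inside the stated ranges has a difference between -0.25 - (-0.75) = 0.50 D and 0.25 - (-1.00) = 1.25 D.
3. If refractive accuracy is reported, measure it from each eye's documented target with one convention for both eyes, for example the proportion of eyes within the stated range. The ranges differ in width (0.50 and 0.25 D), so compare these proportions between arms within eye type, not between eye types.
4. State that the day 17-28 refraction precedes completion of light adjustment in the LAL arm, and describe it by eye.

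Table 15.1 already has both eyes tested, and section 9.2.2 uses dominance to set the order of surgery, so no new visit, test or subject is needed. Confirm that dominance is recorded on the CRF. The cost is some wording, a few more tables and a few more exploratory comparisons, to be labelled as such.

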### **10. ANALYSIS PLAN**

#### ***10.1. Analysis Data Sets***

All subjects who are enrolled in the study will be evaluated for safety. Efficacy analyses will be performed based on data from those eyes where uncomplicated cataract surgery with IOL implantation was completed.

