#### ***13.5. Safety Analyses***

The type, severity, duration and frequency of reported ocular adverse events will be tabulated. Adverse events will also be summarized for events that were considered treatment-related.

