## 15. STANDARD EVALUATION PROCEDURES

**Table 15.1. Proposed Visits and Study Assessments**

(visits are by patient, with both eyes tested)

Activity	Pre-operative	Operative	Postoperative					
	Visit 1	Visit 2a,2b	Visit 3	Visit 4	Visit 5	Visit 6	Visit 7	Visit 8
			POD 17-28	POD 24-42	POD 31-56	POD 38-63	POD 45-70	POD 90
Informed Consent	L,C							
Demographics	L,C							
General Information: Medical History	L,C							
Surgery		L,C						
Manifest refraction	L,C		L,C	L	L	L	L	L,C
Monocular uncorrected distance VA	L,C		L,C	L	L	L	L	L,C
Monocular corrected distance VA	L,C		L,C	L	L	L	L	L,C
Binocular uncorrected and best-corrected distance VA			L,C	L	L	L	L	L,C
Monocular uncorrected and best distance-corrected intermediate VA (66cm)			L,C	L	L	L	L	L,C
Binocular uncorrected and best distance-corrected intermediate VA (66cm)			L,C	L	L	L	L	L,C
Monocular uncorrected and best distance-corrected near VA (40cm)			L,C	L	L	L	L	L,C
Binocular uncorrected and best distance-corrected near VA (40cm)			L,C	L	L	L	L	L,C
Monocular Distance Corrected Defocus Curve								L,C
Binocular Defocus Curve (Dominant eye: plano corrected, non-dominant: -1.00D)								L,C
PRSIQ questionnaire			L,C					L,C
Total ocular, corneal and internal HOA and SA with iTRACE (Both eyes in LAL group and dominant eye for Clareon group)			L	L	L	L	L	L,C
Number of days and post-op office visits from cataract surgery to routine "release of care visit" (i.e. final lock-in for LAL group, 17-28 days after 2nd eye surgery for Clareon group)								L,C
Monitor for Adverse Events and Device Deficiencies		L,C	L,C	L,C	L,C	L,C	L,C	L,C
Complete Exit Form 								L,C

C = Clareon Group; L = LAL group

 Complete Exit Form upon termination of subject participation, or at Visit 8, whichever occurs first.

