## **18. STUDY ENDPOINT CRITERIA**

### ***18.1. Patient Completion of Study***

If a study patient has completed the final visit (Visit 8) of the study, he/she is considered to have completed the study.

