### ***18.3. Patient Termination***

A study patient will be terminated if the study patient develops any severe adverse event that may be related to the study. A study patient will receive appropriate treatment at the discretion of the investigator. Notification of termination will be clearly documented. These study patients are considered to have completed the study and will not be replaced.

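### Section 10.2.1 limits the descriptive efficacy summaries to eyes that complete the study, so early-visit data of later drop-outs go unreported and the natural drop-out check is lost

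*Combined protocol and SAP*

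**What the plan says.** All references are to the combined protocol and SAP.

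- Section 10.2 sets the scope of the summaries: "A summary of the data will be prepared for all measurement time points".
- Section 10.2.1 lists the descriptive statistics and then restricts who is in them: "These summaries will be provided for all eyes completing the study".
- Section 18.1 defines completion: "If a study patient has completed the final visit (Visit 8) of the study, he/she is considered to have completed the study".
- Section 18.3 adds an exception for subjects terminated because of a severe, possibly related adverse event: "These study patients are considered to have completed the study and will not be replaced".
- Section 10.1 defines the efficacy set without reference to follow-up: "Efficacy analyses will be performed based on data from those eyes where uncomplicated cataract surgery with IOL implantation was completed". For safety it says: "All subjects who are enrolled in the study will be evaluated for safety".
- In Table 15.1 the row "Binocular uncorrected and best-corrected distance VA" is scheduled at Visit 3 in both arms, at Visits 4-7 in the LAL arm only, and at Visit 8 in both arms. It is not scheduled before surgery.
- Sections 3 and 8.1 name manifest refraction and the PRSIQ at postoperative days 17-28 as exploratory outcomes. Every primary and secondary outcome is at 3 months.

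**The concern.** Membership of an early-visit summary should depend on what is known at that visit. Here it depends on attending a later one. A subject examined at Visit 3 who leaves before Visit 8 has valid Visit 3 data, belongs to the section 10.1 set, and is still left out of the Visit 3 summary.

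Two things are at stake. First, the day 17-28 refraction and PRSIQ results would be reported as Visit 3 results but would describe only subjects who stayed. Second, Visit 3 is the only visit before Visit 8 at which binocular CDVA is scheduled in both arms. It is the natural place to ask whether those lost saw worse than those who stayed, and whether this differed by arm.

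Informative or unequal loss is plausible on the plan's own terms. The study is unmasked (section 3). LAL subjects can have up to four extra visits (Table 9.2-1). Failure to keep the visit schedule is a ground for discontinuation (section 18.2), and treatment failure is a listed reason for it (section 9.5). The plan contains no missing-data method and no comparison of drop-outs with completers.

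**Working it through.** **1. The plan's own figure.** Inputs from sections 10.2.1 and 11: margin 0.1, assumed difference 0.05, SD 0.1 (all logMAR), power 90%, alpha 0.05.

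n per group = 2 × SD² × (z₀.₉₅ + z₀.₉₀)² / (margin − difference)² = 2 × 0.1² × (1.645 + 1.282)² / 0.05² = 68.5, rounded up to 69.

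This matches the plan with alpha taken as one-sided. The 69 therefore contains no allowance for loss, and the documents give no expected loss rate. The rates below are assumptions.

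**2. Who is in which set.** Take a subject with uncomplicated surgery in both eyes who was measured at Visit 3:

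| Later course | In the 10.1 efficacy set | In the Visit 3 summary under 10.2.1 |
|---|---|---|
| Attends Visit 8 | Yes | Yes (18.1) |
| Lost or withdrawn before Visit 8 | Yes | No |
| Terminated under 18.3 before Visit 8 | Yes | Yes (18.3 counts the subject as completed) |

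Sections 10.1 and 10.2.1 disagree on the second row. The second and third rows are treated differently although neither subject has Visit 8 data. Two statisticians could produce different denominators from this text.

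**3. How many subjects.** Assumed loss between Visit 3 and Visit 8, applied to 138 subjects:

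- 5%: 6.9, about 7 subjects (14 eyes)
- 10%: 13.8, about 14 subjects (28 eyes)
- 15%: 20.7, about 21 subjects (42 eyes)

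**4. Effect on a Visit 3 mean.** Let d be the proportion lost and g the amount by which those lost are worse at Visit 3. The mean of all subjects is the completer mean plus d × g, so the completers-only mean looks better by d × g. With g assumed to be 0.05 to 0.20 logMAR:

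- d = 5%: 0.0025 to 0.010 logMAR
- d = 10%: 0.005 to 0.020 logMAR
- d = 20%: 0.010 to 0.040 logMAR

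This applies within an arm. Only the part that differs between arms distorts a comparison.

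**5. What the sentence does not affect.** The 3-month comparison needs Visit 8 acuity. Suppose those lost were 0.10 logMAR worse, with 10% lost in one arm and 3% in the other. The 3-month difference would shift by 0.10 × (0.10 − 0.03) = 0.007 logMAR. The standard error at full enrolment is 0.1 × √(2/69) = 0.017, so the shift is 0.007 / 0.017 = 0.41 of a standard error, and 7% of the 0.1 margin. That shift would come from missing Visit 8 values. Rewording section 10.2.1 would leave it as it is.

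**The case against.** The strongest reply is that this is one loosely worded sentence with a short reach.

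- It governs only the descriptive summaries. Efficacy analyses follow section 10.1, and at 3 months a subject without Visit 8 data has nothing to summarise. **This stands:** the named outcomes directly affected are exploratory.
- Safety is evaluated in all enrolled subjects, and section 13.5 says: "The type, severity, duration and frequency of reported ocular adverse events will be tabulated". **This stands.**
- Section 10.2.1 already requires the sample size in each continuous summary, and the Exit CRF records the reason for early exit (section 9.2.6). Unequal loss would therefore be visible against 69 per group. **This stands in part:** the number lost would show, but not the acuity of those lost.
- Other acuity may exist: Visits 4-7 in the LAL arm, and examinations at premature exit in either arm. **This stands in part:** Visits 4-7 have no Clareon counterpart, exit examinations are required only where possible, and the completer rule would omit both except for section 18.3 subjects.
- Section 18.3 keeps one potentially informative group in the summaries. **This stands**, but it makes the rule inconsistent between kinds of early exit.

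A reader might infer that drop-outs' data are deleted from every table, or that this sentence biases the non-inferiority result. The documents support neither. Nothing says that data are destroyed, the safety tables are separate, and any bias in the 3-month difference would come from the missing Visit 8 values.

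**Conclusion.** The point holds for the descriptive efficacy summaries before Visit 8. Section 10.2.1, read with section 18.1, conflicts with sections 10.1 and 10.2 and conditions the Visit 3-7 summaries on a later event. The exploratory day 17-28 refraction and PRSIQ outcomes would be reported for later completers only, and the plan would not show the one scheduled pre-Visit-8 binocular CDVA that both arms share for those who left.

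The size is modest and rests on assumed loss: about 7 to 21 subjects omitted at 5-15%, and a Visit 3 arm mean of binocular CDVA too favourable by 0.005 to 0.020 logMAR at 10% loss if those lost were 0.05 to 0.20 logMAR worse. The direction of any between-arm effect is unknown. The primary and secondary 3-month estimates and the safety tables are unchanged. The change is worth making because it removes a contradiction and supplies a check at almost no cost; the primary conclusion does not depend on it.

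**What to change.** 1. Replace the restricting sentence in section 10.2.1 with: *At each visit, summaries include all eyes (subjects for binocular measures and PRSIQ) in the 10.1 set with a measurement at that visit, with the number stated.* This change stands on its own. It aligns the section with 10.1 and 10.2, and the section 18.3 exception then no longer matters for denominators.
2. Add a table of Visit 3 binocular CDVA by arm for subjects with and without Visit 8 data. Classify by whether Visit 8 data exist, not by completion status, so that section 18.3 subjects fall in the right column. Keep it descriptive. At 10% loss each arm has about 7 such subjects (69 × 0.10 = 6.9), and with the plan's SD the standard error of their mean is 0.1 / √7 = 0.038 logMAR. The table can reveal a large gap but cannot exclude a small one.
3. Optional: a repeated-measures sensitivity model of binocular CDVA at Visits 3 and 8 with arm-by-visit terms. It rests on its own missing-data assumption. It also needs the caveat that LAL acuity at Visit 3 is measured around the first UV treatment (Table 9.2-1), before adjustment is complete, while Clareon eyes have no further lens adjustment to come.

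The cost is one sentence and one table from data already scheduled, with no new visits or subjects and no change in sample size. The downside is that denominators differ between visits and must be shown.

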### ***8.2. Methods Used to Minimize Bias***

Patient selection will be based on the patient's interest and the surgeon's opinion as to whether they are a suitable candidate for IOL implantation. Subjects will be randomized to treatment groups.

The measurement of visual acuity will be conducted in a systematic fashion to minimize bias. Individuals conducting visual acuity measures will be instructed to perform the same testing in the same fashion for all subjects, with the same level of encouragement to subjects. Questionnaire instructions will be provided to all patients in a similar manner.

All data collection will be completed through provided Case Report Forms (CRFs) or computer files generated by automated test equipment. All site personnel involved in the study will be trained in regard to conducting study-specific procedures.

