### **10.3. General Statistical Considerations**

The statistical analyses will be performed using R, version 4.2.2 or higher. Any statistical tests of hypotheses will employ a level of significance of alpha=0.05.

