## **11. SAMPLE SIZE JUSTIFICATION**

Assuming a difference in mean visual acuity between groups of 0.05 logMAR^2 and a pooled standard deviation of 0.1 logMAR, the study would require a sample size of: 69 subjects for each group (total sample size of 138 subjects), to achieve a power of 90% and alpha = 0.05.

There is significant uncertainty in the assumptions for mean difference between groups and pooled standard deviation. Therefore, blinded sample size re-estimation is planned. One interim analysis will be conducted after enrollment of 30 subjects in each group (60 subjects total) to re-estimate the sample size.

One interim analysis will look at the variability in each group (biostatistician should be blinded to the groups). Using these values, the required sample size will be re-estimated.

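### The aberration regression and the monocular secondary comparisons have no stated method for the two correlated eyes of one subject

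*Combined protocol and SAP*

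**What the plan says.** - **Randomised unit.** Section 8.2: "Subjects will be randomized to treatment groups". Section 7.1 requires both eyes of each subject to be enrolled, and Table 15.1 has both eyes tested at visits.
- **Efficacy data.** Section 10.1: "Efficacy analyses will be performed based on data from those eyes where uncomplicated cataract surgery with IOL implantation was completed".
- **Summaries.** Section 10.2.1: "These summaries will be provided for all eyes completing the study"; for categorical variables, "summaries will provide the number and percentage of eyes in each category".
- **Tests.** Section 10.2.1: "Differences between parametric variables will be compared using a two-sample t-test". Categorical variables get a two-sample test of proportions. Section 10.3 adds: "Any statistical tests of hypotheses will employ a level of significance of alpha=0.05", without sidedness.
- **Monocular endpoints.** Section 8.1 lists monocular CDVA, UDVA, DCIVA and UIVA at 3 months as secondary outcomes and does not say which eye is analysed.
- **Aberration regression.** Section 10.2.1: "The correlation of total ocular and internal HOAs (especially SA) with monocular DCIVA will be evaluated using regression modelling". Section 8.1 and Table 15.1 specify aberration data from both eyes in the LAL group and the dominant eye only in the Clareon group.
- **Refractive targets.** Section 9.2.2 targets plano ± 0.25 D in the dominant eye and -0.75 to -1.00 D in the non-dominant eye.

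No section mentions a mixed model, GEE, cluster-robust variance or a one-eye rule.

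**The concern.** Two eyes of one person are usually correlated. A two-sample t-test or an ordinary regression on eyes assumes that they are not, and so credits the data with more information than they hold.

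For the regression, the eyes are fixed by the protocol: LAL subjects contribute two each. A plain fit at eye level therefore gives standard errors that are too small when both the aberrations and the acuity residuals are positively correlated between eyes. Section 10.2.1 intends to report which aberrations are statistically significant, so some could be flagged too readily.

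For the four monocular endpoints, the unit is simply open. One analyst could use 69 values per arm and another 138, and they would report different intervals and p-values from the same data. For UDVA and UIVA, pooling would also mix eyes with different refractive targets.

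**Working it through.** **The plan's own figure.** Section 11 assumes a difference of 0.05 and "a pooled standard deviation of 0.1 logMAR"; the margin is 0.1 logMAR. At one-sided alpha 0.05 and 90% power: n = 2 × (1.645 + 1.282)² × 0.1² / (0.1 − 0.05)² = 68.5, rounded up to 69 per group. That reproduces the stated size. It counts subjects, with one binocular value each, so inter-eye correlation does not enter it.

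**Assumptions.** The documents give no inter-eye correlation (ρ), so 0.3 to 0.9 is assumed. Tests are taken as two-sided at 0.05. With 69 subjects per arm there are 138 eyes per arm. In each case, error = 2 × [1 − Φ(1.960/√V)], where V is the true variance divided by the variance that the naive analysis assumes.

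**1. Aberration regression.** Let ρx be the inter-eye correlation of the aberration and ρy that of the DCIVA residual.
- Both arms in one model: 138 LAL + 69 Clareon = 207 eyes, so V = 1 + ρx·ρy × 138/207.
- LAL-only fit: every eye is paired, so V = 1 + ρx·ρy.
- Clareon-only fit: one eye per subject, so there is no inflation.

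| ρx = ρy | V, both arms | Error | V, LAL only | Error |
|---|---|---|---|---|
| 0.3 | 1.060 | 5.7% | 1.09 | 6.0% |
| 0.5 | 1.167 | 7.0% | 1.25 | 8.0% |
| 0.7 | 1.327 | 8.9% | 1.49 | 10.8% |
| 0.9 | 1.540 | 11.4% | 1.81 | 14.5% |

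Simulation of the combined fit (10,000 runs per setting) gave 5.5%, 7.0%, 9.1% and 11.4% for the naive analysis. Cluster-robust errors gave 5.4-5.8% across the settings run, so clustering gains nothing real at 0.3 but matters at higher correlations.

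**2. Monocular CDVA and DCIVA, if both eyes are pooled.** With equal SDs and equal means in the two eyes, V = 1 + ρ. With unequal SDs s₁ and s₂ and equal means, V = (s₁² + s₂² + 2ρs₁s₂)/(s₁² + s₂²). For SDs of 0.1 and 0.2 this is 1 + 0.8ρ.

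| ρ | Equal SD | SD 0.1 and 0.2 |
|---|---|---|
| 0.3 | 8.6% | 7.8% |
| 0.5 | 11.0% | 9.8% |
| 0.7 | 13.3% | 11.7% |
| 0.9 | 15.5% | 13.5% |

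At ρ = 0.1 with equal SDs it is 6.2%. If the test were one-sided at 0.05, the equal-SD column would read 7.5%, 9.0%, 10.4% and 11.6%. Simulation of the pooled t-test (20,000 runs) gave 8.7%, 11.3%, 13.5% and 15.3% two-sided.

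**3. Monocular UDVA and UIVA, if both eyes are pooled.** A fixed gap between dominant and non-dominant eyes widens the within-arm SD that the t-test uses. With equal SDs and the same gap in both arms, V = (1 + ρ)/(1 + gap²/(4·SD²)). Gap and SD are assumptions here.
- Gap 0.3, SD 0.1, ρ = 0.3: V = 1.3/3.25 = 0.40, error 0.2%.
- Gap 0.1, SD 0.2, ρ = 0.9: V = 1.9/1.0625 = 1.788, error 14.3%.

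These are the extremes over gaps 0.1-0.3, SD 0.1-0.2 and ρ 0.3-0.9, so no direction can be claimed.

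**The case against.** The strongest reply is that the plan never says eyes will be pooled in the t-tests. Section 10.1 uses the word eyes for all efficacy data, including binocular acuity, so it can be read as an eligibility filter. The categorical summaries count eyes even though a spectacle questionnaire has no eye. Separate tests by eye role would also fit the text. This stands: for the monocular endpoints the defect is an unstated unit, and the inflation figures hold only under one reading. A reader might infer that the plan commits to an invalid pooled analysis; the documents do not support that.

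A reader might also infer that the trial's main conclusion is at risk. It is not. The primary and all four step-down endpoints are binocular, with one value per subject. No success claim is attached to a monocular endpoint, and the aberration measures are exploratory.

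Two further points are fair. The regression's form is unspecified, so a single error range would mislead; combined and LAL-only fits are therefore both shown. And when every subject contributes both eyes, a pooled difference still estimates the average lens effect over the two eyes. What fails is its standard error and, for uncorrected acuity, its ease of interpretation.

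The reply does not reach the regression. There the protocol itself supplies two eyes per LAL subject and no method for their pairing.

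**Conclusion.** The point holds for supportive and exploratory analyses only. It is firmest for the aberration regression: at eye level and without clustering, two-sided error is about 5.7-11.4% with both arms in one model, or 6.0-14.5% for LAL alone, if both inter-eye correlations are 0.3-0.9. At the low end of that range the effect is negligible.

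For monocular CDVA and DCIVA, the range of 8.6-15.5% (7.8-13.5% with SDs of 0.1 and 0.2) is conditional on pooling and on equal means in the two eyes. For UDVA and UIVA no direction is claimed. That the method is missing is certain from the text; the size of the effect rests on correlations that the documents do not give. It is worth correcting because the remedy is cheap and the study is unmasked, so a unit chosen after the data are seen would invite doubt.

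**What to change.** In section 10.2.1:

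1. **Monocular endpoints.** Analyse them with a mixed model or GEE clustered by subject, with lens, eye role (dominant or non-dominant) and their interaction. Alternatively, name one eye per subject as the tested eye and describe the other. Label these comparisons supportive and unadjusted for multiplicity.
2. **Aberration regression.** Use subject-clustered standard errors or a subject random effect, keeping all measured eyes. State whether the arms are fitted together; if so, include lens and eye role, since only the LAL group contributes non-dominant eyes.

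**Cost.** A few sentences and minor extra R code; no new data, visits or subjects. Intervals widen to their honest width. If the sample-size SD of 0.1 applied to monocular acuity (section 11 does not say so), the half-width per eye role would be 1.98 × 0.1 × √(2/69) = 0.034 logMAR, against an apparent 1.97 × 0.1 × √(2/138) = 0.024 from pooling.

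**Trade-offs.** Testing each eye role separately makes eight unadjusted tests instead of four. If they were independent, the chance of at least one false positive would be 1 − 0.95⁸ = 33.7% against 1 − 0.95⁴ = 18.5%; naming one eye keeps four. Restricting the regression to dominant eyes would also remove the pairing, but it discards 69 LAL eyes that the protocol sets out to measure, so clustering is the better choice.
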